9.3.2 Pharmacokinetic Statistical Methodology

For Part A, the primary parameter for statistical analysis will be t_{max} . The values for t_{max} will be log-transformed and evaluated in a linear mixed-effects model with fixed effects for administration method, period and sequence order (order 1 is derived based on sequences 1 and 3, and order 2 is derived based on sequences 2 and 4), and a random effect for subject. The difference in least squares (LS) means along with the 90% CI will be back-transformed to present the ratios of geometric means and the 90% CI for the comparison of the administration methods (single SC injection [test] and CSII [reference]). This same analysis will be repeated for $AUC(0-t_{last})$, $AUC(0-\infty)$, and C_{max} .

Example SAS code:

```
proc mixed data= ;
  class seqorder period method subject;
  model l_pk = seqorder period method / outpred=resids ddfm=kr;
  random subject;
  lsmeans method / pdiff alpha=0.1;
  ods output lsmeans=lsm;
  ods output diffs=diff;
run; quit;
```

The values of t_{max} will also be analyzed non-parametrically using a Wilcoxon signed-rank test using the SAS procedure PROC UNIVARIATE. Median differences and approximate 90% CIs for the difference will be calculated for the comparisons of the administration methods (single SC injection and CSII).

No formal statistical analysis will be conducted for Part B.

PK parameters will be listed and summarized for both parts of the study.

9.4 Pharmacodynamic Assessment

9.4.1 Pharmacodynamic Analysis

The PD measurements will be derived from the euglycemic clamp procedure, where the glucose infusion rate (GIR) over time is used as a measure of insulin effect. The analyses will be performed according to the Lilly Global PK, PD, and Pharmacometrics Divisional Standard Operating Procedures.

A locally weighted scatterplot smoothing (LOESS) function will be applied to all individual GIR versus time profiles in each treatment group using S Plus® software (Version 8.2 or higher, TIBCO, USA). The fitted data for each subject will be used to calculate the PD parameters: the maximum GIR (R_{max}), the total amount of glucose infused (G_{tot}) over the duration of the clamp procedure, the time of maximum GIR (tR_{max}). Raw (that is, observed) GIR values from each clamp procedure will be used to calculate other PD parameters, such as the time of first change of GIR postdose (tR_{onset}), the time of last measurable GIR (tR_{last}). Other parameters, such as early tR_{max50} , and late tR_{max50} , may also be reported. Parameters will be individually calculated by Eli Lilly and Company and sent to Covance for statistical analysis.

9.4.2 Pharmacodynamic Statistical Methodology

For Part A, the values of tR_{max} will be analyzed non-parametrically using a Wilcoxon signed-rank test using the SAS procedure PROC UNIVARIATE. Median differences and approximate 90% CIs for the difference will be calculated for the comparisons of the administration methods (single SC injection [test] and CSII [reference]).

The PD parameters (R_{max} and G_{tot}) will be log-transformed prior to analysis and a linear mixed-effects model fitted to the data, with administration method, period, and sequence order (order 1 is derived based on sequences 1 and 3, and order 2 is derived based on sequences 2 and 4), as fixed effects and subject as a random effect. For each parameter, the difference in LS means along with the 90% CI will be back-transformed to present the ratios of geometric means and the CI for comparison of the administration methods.

See the [PK statistical methodology](#) for example SAS code.

Other time parameters (tR_{last} , tR_{onset} , early tR_{max50} , and late tR_{max50}) will be analyzed non-parametrically if reported.

No formal statistical analysis will be conducted for Part B.

PD parameters will be listed and summarized for both parts of the study.

Mean daily 4-point self-monitored plasma glucose (SMPG) data will be listed and also summarised for the 5 days prior to period 1, 2 and 3. Figures of mean SMPG prior to periods 1, 2 and 3 will be produced. Profiles prior to meals, bedtime and at 3am will also be produced as appropriate.

Exploratory analyses may be performed for other PD parameters as deemed appropriate.

9.5 Safety and Tolerability Assessments

9.5.1 Adverse events

Where changes in severity are recorded in the Case Report Form (CRF), each separate severity of the adverse event (AE) will be reported in the listings, only the most severe will be used in the summary tables. A pre-existing condition is defined as an AE that starts before the subject has provided written informed consent and is ongoing at consent. A non-treatment emergent AE is defined as an AE which starts after informed consent but prior to dosing. A treatment-emergent AE is defined as an AE which occurs postdose or which is present prior to dosing and becomes more severe postdose.

All AEs will be listed. Treatment-emergent AEs will be summarized by treatment, severity and relationship to the study drug. The frequency (the number of adverse events, the number of subjects experiencing an adverse event and the percentage of subjects experiencing an adverse event) of treatment-emergent adverse events will be summarized by treatment, Medical Dictionary for Regulatory Activities (MedDRA) version 18.0 system organ class and preferred

term. The summary and frequency adverse event tables will be presented for all causalities and those considered related to the study drug. Any serious adverse events will be tabulated.

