7.1.2. Part A (Study Periods 1 and 2)

Subjects will be admitted to the clinical research unit (CRU) on Day -1 of each period and be fasted from 12 hours prior to clamp initiation until completion of the clamp procedure.

All subjects will stop their prestudy U-100, U-200, and/or U-300 insulin dosing at least 15 hours prior to U-500R bolus dosing. Subjects randomized to receive U-500R by SC injection will receive a 100-U U-500R bolus administration by SC injection prior to initiation of the clamp. Subjects randomized to receive U-500R by CSII will have a U-500 OmniPod Insulin Management System (U-500 OmniPod) fitted by a qualified member of CRU staff, which will administer a 12-hour infusion of 4.25 U/h of U-500R, prior to bolus administration of 100 U of U-500R (via the same pump) and initiation of the clamp. The 4.25-U/h U-500R infusion will continue throughout the duration of the clamp following bolus administration by the U-500 OmniPod.

Overnight, between Day -1 and Day 1, all subjects will have their PG stabilized, using an insulin lispro and/or glucose drip, to a target fasting PG concentration of 120 mg/dL (6.7 mmol/L) (with an acceptable range of 100 to 130 mg/dL [5.6 to 7.2 mmol/L]).

Following bolus dose administration (or initiation of bolus dose administration for CSII), subjects will undergo a euglycemic clamp with a maximum duration of 24 hours. Following completion of the clamp procedures, subjects will be provided a meal and will be medically assessed and discharged from the CRU, unless the investigator has any safety concerns. If glucose is still being infused at the time of clamp discontinuation, the subject will be monitored for safety and will remain in the CRU until stable according to investigator judgment (see Section 10.4.1).

Blood samples will be collected prior to and during the clamp procedure (see [Attachment 1](#)) to determine serum immunoreactive insulin (IRI) and C-peptide concentrations for PK and PD analysis.

Following termination of the clamp procedure in Period 1, subjects will resume their prestudy treatment regimen (which may include basal; premixed; and/or basal/bolus U-100, U-200, and/or U-300 insulin regimens with or without antihyperglycemic agents [AHAs] as listed in Inclusion Criterion [5], Section 8.1.1) until their admission to the CRU on Day -1 of Period 2. There will be a washout period of 7 to 21 days between U-500R bolus doses in Periods 1 and 2.

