7.1.3. Part B (Study Period 3)

Following termination of the clamp procedure in Period 2, subjects will transition, as randomized, to TID or BID MDIs of U-500R. Human regular U-500 insulin will be self-administered by the subjects at home under telephone guidance from CRU staff during a telephone visit 2 to 3 days after the end of Period 2 (additional telephone or office visits may be added at the investigator's discretion). Initial U-500R doses will be based on each subject's insulin TDD prior to admission for Period 2, with titration for safety, if necessary, using the formulas given in Section 9.4. There will be 5 to 10 days between the end of Period 2 and the clamp in Period 3 (that is, dosing will begin on up to Day -10 and no later than Day -5 of Period 3) to allow steady state of the U-500R dosing regimen to be achieved. Mean self-monitored plasma glucose (SMPG) will be recorded from Day -5 until admission to the CRU.

Subjects will be admitted to the CRU on Day -1 of Period 3, prior to their pre-evening meal dose, which will be administered by CRU staff, and undergo fasting, PG stabilization, and a 24-hour euglycemic clamp as detailed in Section 7.1.2, with PK sampling as detailed in the Study Schedule ([Attachment 1](#)).

Following termination of the clamp procedure in Period 3 (Day 2), subjects will resume their prestudy insulin treatment regime. Discharge from the CRU will be subject to the same postclamp safety assessments as detailed in Section 7.1.2 and Section 10.4.1. Follow-up will occur 7 to 28 days after the end of Period 3 when safety procedures will be conducted and insulin use and dose will be recorded as detailed in the Study Schedule ([Attachment 1](#)).

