Clinical laboratory tests	X	X (Period 1 only)								X	See Attachment 2 , Clinical Laboratory Tests, for details.
Pregnancy test	X	X				X				X	Serum pregnancy test will be performed at screening. Urine pregnancy test will be performed at every admission period and at poststudy, if applicable.
Physical exam	X										After screening, medical assessment only performed to include medical review and targeted examination, as appropriate.
12-lead ECG	X		Predose	24 h ^c				Predose	24 h	X	

	Screening	Periods 1 and 2 ^a			Period 3				Follow-up	Comments
		Days			Days					
Procedure	Up to 28 days prior to Period 1	-1	1	2	-10 ^b to -2	-1	1	2	7 to 28 days after discharge or early discontinuation	
SMPG					X					4-point SMPG to be conducted daily throughout the study, except whilst resident in the CRU. Mean SMPG for the 5 days prior to Period 3 will be collected in the eCRF.
Overnight PG stabilization		X				X				PG stabilized using an insulin lispro and/or glucose drip.
Euglycemic clamp			X				X			
Pharmacogenetic sample		X (predose)								Single sample for pharmacogenetic analysis taken on Day -1 of Period 1.
PK and C-peptide samples		-12, -8, -4 h	-0.5, 0 (predose), 0.5, 1, 2, 3, 4, 5, 6, 7, 8, 12, 16 h	24 h			-0.5, 0 (predose), 0.5, 1, 2, 3, 4, 5 (predose for TID), 6, 7, 9, 11 (predose), 12, 13, 15, 18 h	24 h		Sampling times are relative to the time of the start of study treatment morning bolus administration (0 h). Sampling times for Period 3 are relative to the time of breakfast (0 hr), lunch (5 hr) and dinner (11 hr).

Abbreviations: BG = blood glucose; BID = twice daily; CRU = clinical research unit; CSII = continuous subcutaneous insulin infusion; ECG = electrocardiogram; PG = plasma glucose; PK = pharmacokinetics; SMPG = self-monitored plasma glucose; TDD = total daily dose; TID = thrice daily; U-500R = human regular U-500 insulin.

- a There may be 7 to 21 days between bolus doses in Period 1 and Period 2.
- b There may be 5 to 10 days between the end of Period 2 and clamp initiation in Period 3 (Day 1), that is BID or TID dosing may begin on Day -10 through Day -5.
- c Clamp procedure in Periods 1 and 2 are of a maximum duration of 24 hours. Vital signs and ECGs will be conducted at the end of the clamp procedure.
- d CSII period only, taken prior to initiation of 12-hour U-500R infusion.

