6. TREATMENTS

The following is a list of the study treatment abbreviations that will be used in the TFLs.

| Study Treatment Name | Treatment order in TFL |
|---------------------------|------------------------|
| 100-U bolus U-500R (SC) | 1 |
| 100-U bolus U-500R (CSII) | 2 |
| U-500R (BID) | 3 |
| U-500R (TID) | 4 |

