9.5.4 Vital signs

Vital signs data will be summarized by treatment together with changes from baseline, where baseline is defined as Day 1 predose of the relevant period. Figures of mean vital signs and change from baseline profiles will be presented. Furthermore, values for individual subjects will be listed.

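### Adverse events that start while subjects are back on prestudy insulin can be counted only under a U-500R treatment

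*SAP*

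**What the plan says.** SAP section 9.5.1 defines the events: "A treatment-emergent AE is defined as an AE which occurs postdose", or one already there before dosing that worsens afterwards. It then says how they are tabulated: "Treatment-emergent AEs will be summarized by treatment, severity and relationship to the study drug". No end of window is given. SAP section 6 lists the treatment names for the tables, figures and listings. There are four, all U-500R, with no entry for the interval between Periods 1 and 2 or for follow-up.

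The protocol describes what subjects take in those intervals. After the Period 1 clamp, "subjects will resume their prestudy treatment regimen" until admission for Period 2 (section 7.1.2). After the Period 3 clamp, "subjects will resume their prestudy insulin treatment regime", with follow-up 7 to 28 days later (section 7.1.3). After the Period 2 clamp they go straight to TID or BID U-500R. The prestudy regimen is itself high-dose: a total daily dose of at least 150 U, or at least one dose above 100 U (section 8.1.1).

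Adverse events are reported from the first dose of investigational product (section 10.4.2), and serious events are collected to the last study visit (section 10.4.3).

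**The concern.** Carrying an event back to the last treatment is reasonable when the washout is drug-free. Here the washout, and the follow-up, are filled with another insulin at high dose. An open-ended window and four U-500R labels leave an event that starts in those weeks nowhere else to go.

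The window also depends on the period. A subject given SC or CSII in Period 1 contributes 7 to 21 days to that column; a subject given the same treatment in Period 2 contributes about one day before Part B dosing starts. The SAP reports one percentage of subjects over both.

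At stake is the meaning of the by-treatment incidence figures. Safety is part of the interim analysis, planned after about 12 subjects complete Part A and meant to inform a Phase 3b trial (SAP section 10), so the Part A columns will be used before the study ends.

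**Working it through.** The plan gives no figure to reproduce here. The check is how much of each window, as the SAP's text leaves it, is spent on prestudy insulin.

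**Inputs**
- Gap between Period 1 and Period 2 boluses: 7 to 21 days (Protocol 7.1.2).
- Part A clamp: at most 24 h; prestudy insulin stopped at least 15 h before the next bolus (Protocol 7.1.2).
- Part B lead-in: 5 to 10 days, then a 24-hour clamp (Protocol 7.1.3). The synopsis allows up to 12 days of TID or BID dosing.
- Follow-up: 7 to 28 days after Period 3 (Protocol 7.1.3).

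**Period 1 window, bolus to bolus**

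Share = (24 × gap − 24 − 15) / (24 × gap), taking a full 24-hour clamp.
- 7 days: (168 − 39)/168 = 129/168 = 77%.
- 21 days: (504 − 39)/504 = 465/504 = 92%.

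Given a full-length clamp these are upper figures, because the stop is at least 15 h. Counting all time after the clamp instead gives 6/7 = 86% to 20/21 = 95%, but that includes the hours after prestudy insulin has been stopped.

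**After Period 2**

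The share is zero, because Part B dosing follows the clamp.

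**Part B window, first TID or BID dose to follow-up**

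Share = follow-up / (days on U-500R + follow-up).
- Smallest: 7/(12 + 7) = 7/19 = 37% with the synopsis maximum of 12 days, or 7/(10 + 1 + 7) = 7/18 = 39% with the 10-day lead-in plus the clamp day.
- Largest: 28/(5 + 1 + 28) = 28/34 = 82%.

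**Balance between treatments**

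SC occupies Period 1 in sequences 1 and 3, CSII in sequences 2 and 4. If the sequences fill about equally, each column pools about half its subjects with a 7 to 21 day window and half with about one day. BID and TID have the same follow-up rule.

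**Which events enter**

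Severe hypoglycemia is reported as a serious adverse event and enters the tables. Non-severe hypoglycemia is kept out of the adverse event records (Protocol 10.4.4). SAP 9.5.5 lists hypoglycemic events and summarizes them only if appropriate, with no attribution rule.

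**The case against.** The SAP nowhere says that events are carried forward to the last treatment. That is inferred from an open window, tabulation by treatment and the list of labels. The table shells are a separate document not available here and might add a category or a cut-off. This stands as a limit on the wording, but SAP 9.5.1 and 6 as they read provide no other place for these events, and a rule of this kind belongs in the SAP.

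The related-to-study-drug tables and the full listings let a reader separate some of these events. That also stands, in part: the all-causality tables remain mixed.

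There is little comparative bias, and no inferential safety analysis is planned (SAP 9.5.7). This is right. A reader might infer that the SC versus CSII comparison is biased by the prestudy-insulin weeks; the four-sequence design does not support that.

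A reader might also infer that the first 12 h of CSII exposure (4.25 × 12 = 51 U) is lost or counted under SC. The label beginning "100-U bolus U-500R (CSII" names only the bolus, and SAP 9.5.4 sets the vital-sign baseline with the words "where baseline is defined as Day 1 predose of the relevant period". But that baseline governs vital signs, not adverse events. Protocol Table IBHG.9.1 lists the basal infusion as part of the CSII investigational regimen, and reporting starts at the first dose of investigational product. The documents favor counting the infusion as dosing; one clarifying line is enough.

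Nor do they show that the −12 h vital signs go unused. The schedule describes these as "CSII period only, taken prior to initiation of 12-hour U-500R infusion", and SAP 9.5.4 does not exclude them from its summaries or listings. With no SC counterpart, an extra change-from-−12 h table would be a preference.

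**Conclusion.** The point holds as a gap in the attribution rule. Adverse events that start on prestudy insulin can be counted only under SC, CSII, BID or TID, in windows where prestudy insulin accounts for up to 77% to 92% (Period 1) and about 37% to 82% (first Part B dose to follow-up) of the time. The effect is on each regimen's absolute incidence and on any Part A versus Part B reading.

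It would go too far to say that every post-dose event is misreported: non-severe hypoglycemia never enters the adverse event tables and is touched only if the optional summary is made.

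The conclusion assumes that the table shells add no cut-off or category, and its balance statement assumes roughly equal sequences. The percentages are shares of time, not of events; the documents give no adverse event rates, so no event counts can be derived. This is a worthwhile and cheap improvement, and the t_max analysis is not affected.

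**What to change.** In SAP sections 6 and 9.5.1:

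1. Add a prestudy insulin / follow-up category to the treatment list.
2. Define each U-500R analysis window from the first U-500R of the period to the later of CRU discharge or 24 h after the last U-500R, or to the next study treatment if sooner. The 24 h is the upper duration of activity given in Protocol 5.1. For CSII, state that the window opens with the 4.25 U/h infusion, in line with Table IBHG.9.1.
3. Keep a later-onset event under the causative treatment if the investigator judges it related to study drug or device, so that delayed pump-site reactions, for example, are not moved out of CSII.
4. Use the same windows for any hypoglycemia summary.
5. Keep the last-treatment tabulation as a supporting table.

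A cut at discharge alone would be too early. The Period 3 schedule places the evening dose at 11 h and the clamp ends at 24 h, so 24 h after that dose runs to 35 h, or 11 h past the clamp.

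The change is to SAP and shell wording. Dose times are already recorded, and the SAP's own definition already needs event onset relative to dosing. The costs are one more column, fewer events per U-500R column, and some late events classed as prestudy insulin. The windows will also differ in length: in Period 1, about 24 h after an SC bolus (longer if discharge is later), against 12 + 24 + 24 = 60 h for CSII with a full clamp. A footnote giving each window's length would make that visible.

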10.4.2. Adverse Events

Lilly has standards for reporting AEs that are to be followed regardless of applicable regulatory requirements that may be less stringent.

Study site personnel will record the occurrence and nature of each subject's preexisting conditions, including clinically significant signs and symptoms of the disease under treatment in the study.

Cases of pregnancy that occur during maternal or paternal exposures to the investigational product and/or drug delivery system should be reported. Data on fetal outcome and breast-feeding are collected for regulatory reporting and drug safety evaluation.

After the informed consent form (ICF) is signed, site personnel will record any change in the condition(s) and the occurrence and nature of any AEs. All AEs related to protocol procedures are reported to Lilly or designee.

Any clinically significant findings from ECGs, labs, vital sign measurements, or other procedures, should be reported as an AE to Lilly or its designee.

In addition, all AEs occurring after the subject receives the first dose of the investigational product must be reported to Lilly or its designee via eCRF.

Investigators will be instructed to report to Lilly or its designee their assessment of the potential relatedness of each AE to protocol procedure, studied disease state, investigational product, and/or drug delivery system via eCRF.

The investigator will decide whether he or she interprets the observed AEs as either related to disease, to the study medication, study procedure, drug delivery system, or other concomitant treatment or pathologies. To assess the relationship of the AE to the investigational product, the following terminologies are defined:

- **Related:** a direct cause and effect relationship between the study treatment and the AE is likely.
- **Possibly related:** a cause and effect relationship between the study treatment and the AE has not been demonstrated at this time and is not probable, but is also not impossible.
- **Unrelated:** without question, the AE is definitely not associated with the study treatment.

As per Lilly's standard operating procedures, all "related" and "possibly related" AEs and SAEs will be defined as related to the investigational product.

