11.2.6. Safety Analyses

11.2.6.1. Clinical Evaluation of Safety

All investigational product and protocol procedure AEs will be listed, and if the frequency of events allows, safety data will be summarized using descriptive methodology.

The incidence of symptoms for each treatment will be presented by severity and by association with investigational product, study procedure, or drug delivery device, as perceived by the investigator. Symptoms reported to occur prior to the first dose will be distinguished from those reported as new or increased in severity during the study. Each symptom will be classified by the most suitable term from the medical regulatory dictionary.

The number of investigational product-related SAEs will be reported.

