11.2.6.2. Statistical Evaluation of Safety

Safety parameters that will be assessed include safety laboratory parameters, vital signs, and ECG parameters. The parameters will be listed and summarized using standard descriptive statistics. Additional analysis will be performed if warranted upon review of the data.

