9.5.3 Clinical laboratory parameters

All clinical chemistry, hematology and urinalysis data will be listed. Additionally, clinical chemistry, hematology and urinalysis data outside the reference ranges will be listed.

Values for any clinical chemistry, hematology and urinalysis values outside the reference ranges will be flagged on the individual subject data listings.

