9.5.6 Other assessments

Body weight will be listed. Change in weight and BMI from period 1 to period 2, and from period 2 to period 3 will be listed and summarized.

Change in total daily dose (Units and Units/kg) from pre-Period 3 U-100 to Period 3 U-500R will be listed.

All other safety assessments not detailed in this section will be listed but not summarized or statistically analyzed.

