11. CHANGES FROM THE PROTOCOL SPECIFIED STATISTICAL ANALYSES

There were no changes from the protocol specified statistical analyses.

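### The SAP omits adverse-event attribution to device and procedure, and laboratory and ECG summaries, that the protocol promises, yet declares no changes from the protocol

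*SAP*

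**What the plan says.** **Protocol.** Section 11.2.6.1 has the incidence of events for each treatment presented by severity and "by association with investigational product, study procedure, or drug delivery device, as perceived by the investigator". The data for this are collected: under section 10.4.2 investigators give their "assessment of the potential relatedness of each AE to protocol procedure, studied disease state, investigational product, and/or drug delivery system via eCRF". Section 11.2.6.2 names laboratory, vital-sign and ECG parameters and says "The parameters will be listed and summarized using standard descriptive statistics".

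**SAP.** Section 9.5.1 says "Treatment-emergent AEs will be summarized by treatment, severity and relationship to the study drug". It provides two sets of adverse-event tables, one for all causalities and one for events considered related to study drug. Section 9.5.3 says "All clinical chemistry, hematology and urinalysis data will be listed", adds listing and flagging of out-of-range values, and specifies no summary. Section 9.5.4 summarises vital signs by treatment with change from baseline. Section 9.5 has no ECG subsection, so the closing rule of 9.5.6 applies: "All other safety assessments not detailed in this section will be listed but not summarized or statistically analyzed". Section 9.1 limits summary statistics to data for which the SAP details them.

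**Precedence.** SAP section 3 says that the SAP overrides the protocol's statistical considerations and that substantial differences will be identified. Section 11 then states "There were no changes from the protocol specified statistical analyses".

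**The concern.** The controlling document removes safety outputs that the protocol promises and says that nothing has changed. A reader who relies on SAP section 11 would expect the protocol's safety tables in the study report and would not find them.

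The attribution table is the most useful of the missing outputs. Part A compares a syringe injection with delivery by a pump that protocol 9.2 describes as not yet on the market. The protocol treats device causality as a category of its own: it is recorded separately for each event (10.4.2), pump conditions needing intervention have a dedicated serious outcome (10.4.3), and the pump is singled out in complaint handling (10.4.7). The SAP carries none of this into a table. At stake are the completeness and traceability of descriptive safety reporting, not any efficacy or pharmacokinetic conclusion.

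**Working it through.** The plan gives no figure to reproduce, so the check is a comparison of texts.

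**Step 1. Promised output against SAP output.**

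| Output | Protocol | SAP | Kept? |
|---|---|---|---|
| Adverse events by association with device and procedure | 11.2.6.1: yes, for each treatment | 9.5.1: study drug only | No |
| Laboratory summaries | 11.2.6.2: yes | 9.5.3: listings and flags | No |
| ECG summaries | 11.2.6.2: yes | 9.5.6 residual rule: listing only | No |
| Vital-sign summaries | 11.2.6.2: yes | 9.5.4: by treatment, with change from baseline | Yes |

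Three of four are missing. SAP 9.1 rules out reading them back in, because a summary not detailed in the SAP is not produced. The SAP abbreviation list defines two QT corrections that no SAP section uses, which would fit an oversight over ECGs but does not prove one.

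**Step 2. Where a treatment-emergent event appears under SAP 9.5.1, by the investigator's attribution.**

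| Attribution | Listing | All-causality tables by treatment | Drug-related tables |
|---|---|---|---|
| Drug only | Yes | Yes | Yes |
| Drug and device | Yes | Yes | Yes, but not distinguishable from drug only |
| Device only | Yes | Yes | No |
| Procedure only | Yes | Yes | No |

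No event is lost. What is lost is the tabulated attribution to device or procedure.

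**Step 3. Is this an artefact of document versions?** SAP section 3 cites the protocol and amendment (a), and the current protocol is amendment (b). The amendment (b) summary shows no revision of section 11.2.6, so the mismatch does not appear to come from that amendment.

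**Step 4. What data the omitted summaries would use.** Attachment 1 schedules an ECG before dosing and at the end of the clamp in each period: 2 × 3 = 6 per subject, or 6 × 24 = 144 in 24 completers. This describes the volume of data left unsummarised and measures no bias. Laboratory panels are scheduled at screening, on Day -1 of Period 1 and at follow-up. No panel falls between treatments, so a change from Day -1 of Period 1 to follow-up spans Parts A and B and cannot be assigned to SC, CSII, TID or BID.

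**The case against.** The strongest reply is that pump harm can still be seen. The all-causality tables are given by treatment, system organ class and preferred term, CSII is a separate treatment (SAP section 6), and the design gives each subject both methods. An excess of infusion-site events under CSII would show there. All events are listed and serious events tabulated. This stands. A reader might infer from the omission that pump-related harm cannot be detected, and the documents do not support that.

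A reader might also infer that the drug-related tables favour CSII, because only CSII uses the pump. That is not shown either. Procedure-related events can arise under both methods. The protocol's category is the delivery system, and SC doses use a specified syringe and needle (9.2), so delivery-related events can occur under SC too. Protocol 10.4.2 reserves the unrelated category for events that are certainly not associated with study treatment and counts possibly related events as related, which makes the class of device-only events narrow.

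Clinically significant ECG and laboratory findings are reported as adverse events (10.4.2, 10.4.5.4), so they reach the tables when treatment-emergent. This stands as mitigation. The laboratory and ECG omissions have no bearing on pump harm.

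The promise is also partly conditional: 11.2.6.1 makes summaries of safety data depend on event frequency, and the synopsis allows discretion. But the sentence on association has no condition of its own, 11.2.6.2 has none, and the SAP invokes neither. A condition on event frequency would not explain dropping scheduled ECG and laboratory summaries.

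Finally, the separate table shells might contain the missing tables. They are not available here, and SAP 9.1 limits summaries to those the SAP details.

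**Conclusion.** The mismatch is real. The SAP omits three of the four safety outputs checked, and its statement of no changes is incorrect as written. The practical effect is limited: attribution to device or procedure cannot be read from any related-event table, while the events themselves remain in the listings and the all-causality tables. The number of device-only or procedure-only events cannot be estimated from the documents, and no direction of bias is established. No primary or secondary objective is affected. Severity is minor.

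This rests on two assumptions: that SAP 9.1 and 9.5.6 are applied as written, and that the table shells do not quietly restore the missing outputs.

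**What to change.** - **SAP 9.5.1:** add treatment-emergent summary and frequency tables, by treatment, for events related to the drug delivery device and for events related to study procedure, using the relatedness already reported via eCRF.
- **SAP 9.5, new ECG subsection:** add descriptive summaries of ECG parameters before dosing and at the end of the clamp, by treatment.
- **SAP 9.5.3:** add descriptive laboratory summaries by visit, overall and not by treatment, for the reason given in Step 4.
- **SAP 11:** declare and justify any of these that is not restored.

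The cost is a few descriptive tables and some SAP wording. The attribution tables need no new data. For ECGs, first confirm that interval values are entered in the database: protocol 10.4.5.4 says only that the records are stored at the site.
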